#### **5.1 Description & Packaging**

Everolimus (RAD001) is an inhibitor of mTOR, and is FDA-approved as an antineoplastic agent. The chemical name of everolimus is (1R, 9S,12S,15R,16E,18R,19R, 21R, 23S, 24E, 26E, 28E,30S, 32S,

CONFIDENTIAL

This document and information is the property of the NYU School of Medicine and Langone Medical Center. Do not disclose or use except as authorized in writing by the study IND sponsor

35R)-1,18-dihydroxy-12-[(1R)-2-[(1S,3R,4R)-4-(2-hydroxyethoxy)-3-methoxycyclohexyl]-1-methylethyl]-19,30-dimethoxy-15,17,21,23,29,35-hexamethyl-11,36-dioxa-4-aza-tricyclo[30.3.1.04,9]hexatriaconta-16,24,26,28-tetraene-2,3,10,14,20-pentaone. The molecular formula is C53H83NO14 and the molecular weight is 958.2.

For this study, everolimus will be supplied as dispersal tablets of 2.0, 3.0, 5.0 mg strength. The drug will be supplied by Novartis at no charge for study enrollment to patients enrolled in treatment group at NYU CEC

The starting dose of everolimus for treatment patients will be 4.5 mg/m^2 once daily; adjust to attain trough concentrations of 5-15ng/ml. The dose will be adjusted for co-medications as outlined in the section immediately below.

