#### **CYP3A4 and/or P-glycoprotein (PgP) Inhibitors**

Patients will be excluded if using strong CYP3A4 inhibitors (e.g., ketoconazole, itraconazole, clarithromycin, atazanavir, nefazodone, saquinavir, telithromycin, ritonavir, indinavir, nelfinavir, voriconazole). If the patient is receiving a co-administered drug with moderate CYP3A4 and/or PgP inhibitors (e.g., amprenavir, fosamprenavir, aprepitant, erythromycin, fluconazole, verapamil, diltiazem), the everolimus dose will be reduced by approximately 50% to maintain trough concentrations of 5 to 10 ng/mL. If dose reduction is required for patients receiving 2.5 mg daily, alternate day dosing will be used. Subsequent dosing will be individualized based on therapeutic drug monitoring in subject on everolimus for sufficient duration. No moderate or strong CYP3A4 and/or PgP inhibitor will be added or discontinued during the study period.

Patients taking one concomitant strong CYP3A4 inducer for seizure control (e.g., phenytoin, carbamazepine, phenobarbital) will be allowed in the study. Patients taking more than one strong CYP3A4 inducer will be excluded. For patients requiring a concomitant strong CYP3A4 inducer (an Enzyme-Inducing Antiepileptic Drug (EIAED), we will double the everolimus dose from that prescribed in Table 2. Subsequent dosing should be individualized based on therapeutic drug monitoring if the patient is treated with everolimus for sufficient duration. No EIAED will be discontinued during the study.

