#### **Using an oral syringe:**

- Place the prescribed dose of everolimus tablets for oral suspension into a 10-mL syringe. Do not exceed a total of 10 mg per syringe.

If higher doses are required, prepare an additional syringe. Do not break or crush tablets.

- Draw approximately 5 mL of water and 4 mL of air into the syringe.
- Place the filled syringe into a container (tip up) for 3 minutes, until the everolimus tablets for oral suspension are in suspension.
- Gently invert the syringe 5 times immediately prior to administration.
- After administration of the prepared suspension, draw approximately 5 mL of water and 4 mL of air into the same syringe, and swirl the contents to suspend remaining particles. Administer the entire contents of the syringe.

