#### **5.3.2 Dose Adjustments**

There only planned dose adjustments will be in patients taking the drug for 3. Patients will be started on a set dose of everolimus based on their BSA ( $m^2$ ) and whether or not they are taking an EIAED. For those subjects taking everolimus for 3 weeks, a serum level will be obtained between days 10-12. If the result is in desired range (5-10 ng/ml) for patient receiving study medication, the recommendation will be no change. If the value is between 3-5 ng/ml, the dose will be increased by 2.0 mg/ $m^2$ /day and if the value is less than 3 ng/ml, the recommendation will be dose will be increased by 3.0 mg/  $m^2$ /day. If the value is between 10-13 ng/ml, the dose will be decreased by 2.0 mg/ $m^2$ /day. If the value is above 13 ng/ml, the dose will be decreased by 3.0 mg/ $m^2$ /day.

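### The fixed everolimus reductions in Section 5.3.2 give a negative or unmakeable dose for 21-day patients started at half dose because of a moderate CYP3A4/PgP inhibitor

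*Combined protocol and SAP*

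**What the plan says.** The standard start is 4.5 mg/m² once daily (Section 5.1). For a patient on a moderate CYP3A4 and/or PgP inhibitor, Section 5.1 says "the everolimus dose will be reduced by approximately 50% to maintain trough concentrations of 5 to 10 ng/mL". The interacting drug must stay unchanged while the patient is on study. The same paragraph adds "If dose reduction is required for patients receiving 2.5 mg daily, alternate day dosing will be used" and "Subsequent dosing will be individualized based on therapeutic drug monitoring in subject on everolimus for sufficient duration".

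Section 5.3.2 has three-week patients sampled on days 10–12 and sets 5–10 ng/mL as the desired range. It describes the starting dose by BSA and "whether or not they are taking an EIAED"; inhibitor use is not mentioned. The two downward steps, both in mg/m²/day, are "If the value is between 10-13 ng/ml, the dose will be decreased by 2.0" and "If the value is above 13 ng/ml, the dose will be decreased by 3.0".

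On supply, Section 5.1 states "everolimus will be supplied as dispersal tablets of 2.0, 3.0, 5.0 mg strength", and the syringe instructions say "Do not break or crush tablets". Tables 3 and 4 give 2.5 mg daily as the lowest dose level, with discontinuation below it, in rows about recurrent toxicity. Visit 2a tells staff to adjust the dose using the steps already described.

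**The concern.** The reductions are absolute amounts per m², but the starting dose differs fourfold between the lowest group (2.25 mg/m²) and the highest (9 mg/m², doubled for an enzyme-inducing antiepileptic drug, EIAED). A step that is sensible at 4.5 mg/m² can exceed the whole dose at 2.25 mg/m².

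For a 21-day patient the day 10–12 sample is the one planned point at which a trough above target is brought down before surgery. The inhibitor cannot be withdrawn, so the everolimus dose is the only lever. The next scheduled level is on the day of surgery, so whatever dose is chosen is not checked beforehand (this is true of every adjusted 21-day patient). What is at stake is consistent handling of an over-target level: reduce, hold or stop.

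**Working it through.** The plan gives no worked example of these steps, so there is no figure of its own to reproduce. The check is direct arithmetic on the nominal dose.

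**Inputs.** Start 4.5 mg/m², halved for a moderate inhibitor and doubled for an EIAED (5.1); reductions 2.0 and 3.0 mg/m²/day (5.3.2); tablets of 2, 3 and 5 mg, not to be broken (5.1); floor 2.5 mg/day (Tables 3 and 4); the BSA formula in 5.3. Body sizes are assumed, because the documents give none.

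**Step 1: dose left after each reduction** (reduction as a share of the start in brackets).

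| Group | Start, mg/m² | 10–13 ng/mL (−2.0) | Above 13 ng/mL (−3.0) |
|---|---|---|---|
| Standard | 4.5 | 2.5 (44%) | 1.5 (67%) |
| EIAED | 9.0 | 7.0 (22%) | 6.0 (33%) |
| Moderate inhibitor | 4.5 × 0.5 = 2.25 | 0.25 (89%) | −0.75 (133%) |

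Only the inhibitor group fails.

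**Step 2: can 0.25 mg/m² be made?** The smallest schedule with unbroken tablets, daily or alternate-day, is 2 mg every other day, an average of 1 mg/day. That needs a BSA of 1 / 0.25 = 4.0 m². By the 5.3 formula, a child of 12 kg and 87 cm has 0.526 m² and an adult of 70 kg and 175 cm has 1.848 m². Their computed doses are 0.25 × 0.526 = 0.13 mg/day and 0.25 × 1.848 = 0.46 mg/day, both well under 1 mg/day.

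**Step 3: sensitivity to the approximate halving.** Take a cut of 40% to 60% (assumed range).

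- 40% cut, start 2.7 mg/m²: 2.7 − 2.0 = 0.7 and 2.7 − 3.0 = −0.3.
- 60% cut, start 1.8 mg/m²: 1.8 − 2.0 = −0.2 and 1.8 − 3.0 = −1.2.

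The 3.0 step is negative for any start below 3.0 mg/m², that is, unless at least 3.0 / 4.5 = 67% of the standard dose is kept. The best case for the 2.0 step is 0.7 × 1.848 = 1.29 mg/day, which alternate-day tablets can approximate only in a large patient.

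**Step 4: the 2.5 mg/day floor.** Reaching it at 0.25 mg/m² needs 2.5 / 0.25 = 10 m². The halved starting dose is itself under 2.5 mg when BSA is below 2.5 / 2.25 = 1.11 m².

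**Step 5: reductions scaled to the halved start.** 2.25 − 1.0 = 1.25 mg/m² (1.0 / 2.25 = 44%) and 2.25 − 1.5 = 0.75 mg/m² (1.5 / 2.25 = 67%), the same proportions as in standard-dose patients. The BSA needed to stay at or above a floor is:

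| Floor | At 1.25 mg/m² | At 0.75 mg/m² |
|---|---|---|
| 1 mg/day (2 mg alternate days) | 0.80 m² | 1.33 m² |
| 2.5 mg/day | 2.0 m² | 3.33 m² |

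**The case against.** The strongest reply is that Section 5.1 already takes these patients out of the fixed steps. Its individualization sentence follows directly on the halved dose, is specific to that group, and could be read as prevailing over a general rule that never mentions inhibitors. The dosing paragraph of Section 5.2 also refers inhibitor patients to 5.1 and describes adjustments as permitted, and 5.3.2 words two of its outcomes as recommendations.

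This weakens the point without removing it. Section 5.1 says nearly the same about EIAED patients, whom 5.3.2 does name and cover, so the sentence is not written as an exemption. The two outcomes worded as recommendations are no change and the larger increase; both decreases are stated as what will happen. Visit 2a sends staff to the written steps, and 5.1 offers no step of its own.

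A reader might infer that staff would have nothing to go on and must improvise. The documents do not support that: individualization in 5.1 and the discontinuation rule in Tables 3 and 4 both point towards holding or stopping, although the tables are about toxicity rather than drug levels.

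A reader might also infer that the alternate-day provision in 5.1 contradicts the floor in Tables 3 and 4. The triggers differ (an interacting drug in one, recurrent toxicity in the other), and Table 4 itself expresses its floor as an every-other-day schedule. No firm conflict is shown.

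It is also fair that whole tablets require rounding throughout the protocol, not only here, and that few patients can be affected.

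**Conclusion.** Wrong as written; minor. Applied literally, 5.3.2 gives −0.75 mg/m² above 13 ng/mL and 0.25 mg/m² at 10–13 ng/mL for a patient started at 2.25 mg/m². The first is not a dose, and the second cannot be made from the supplied tablets below a BSA of 4.0 m².

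This rests on the nominal per-m² dose, because the plan gives no rule for rounding to tablets; a start of 3.0 mg/m² or more would not go negative. With the halving read as 40–60%, the 3.0 step stays negative throughout.

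Reach is very small: 21-day patients (1–3 by Table 2, 6 by the text of 5.2, out of 9 treated) who also take a moderate inhibitor and have a trough above 10 ng/mL. The number is unknown and may be zero.

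A reader might go further and infer that the increases for EIAED patients are mis-scaled too. The documents give no relation between dose and trough, so that is not supported. Nor does the point touch the sample size or the stopping rules.

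**What to change.** In Section 5.3.2, for patients started at the halved dose:

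1. Use reductions of 1.0 mg/m²/day at 10–13 ng/mL and 1.5 mg/m²/day above 13 ng/mL.
2. Convert to mg and round down to a dose that whole tablets can make, daily or every other day.
3. Stop everolimus if the result falls below one stated lowest dose for level-based reductions. The choice of that dose is the sponsor's.

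If the sponsor chooses 2.5 mg/day, nearly all of these patients would stop, so 5.3.2 can say just that: moderate inhibitor and trough above 10 ng/mL, stop. The plan should then also say how patients with a BSA below 1.11 m², whose halved starting dose is already under 2.5 mg, are handled. If the lowest dose is 2 mg on alternate days, the smallest patients would still stop, at the 1 mg/day BSA limits shown in the working.

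A sentence saying that 5.3.2, as amended, governs level-based changes for inhibitor patients would settle its relation to 5.1. The cost is a few sentences, with no extra visits, samples or patients.

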Diagnosis and Main Inclusion Criteria	1. Female and male patients, age 2 year to 50 years 2. Diagnosis: treatment resistant epilepsy ( $\geq 2$ failed anti-epileptic drug [AED] treatment regimens) and either: 

• Tuberous Sclerosis Complex (TSC)

• Focal Cortical Dysplasia (FCD) on MRI

Number of Subjects in comparison control group	12 subjects

CONFIDENTIAL

This material is the property of the NYU School of Medicine and Langone Medical Center. Do not disclose or use except as authorized in writing by the study IND sponsor

Diagnosis and Main Inclusion Criteria	

1. Female and male patients, age 2 year to 50 years

2. Diagnosis: treatment resistant epilepsy (<math>> 2</math> failed anti-epileptic drug [AED] treatment regimens) undergoing routine surgery

• Tuberous Sclerosis Complex (TSC)

• Focal Cortical Dysplasia (FCD) on MRI

Study Product, Dose, Route, Regimen	
Everolimus:
 

• Patients NOT taking EIAEDs: The starting dose of everolimus for treatment patients will be <math>4.5 \text{ mg/m}^2</math> once daily; adjust to attain trough concentrations of 5-15ng/ml. The dose will be adjusted for certain co-medications (see below).

• Patients TAKING CYP3A4 and/or P-glycoprotein (PgP) Inhibitors Patients will be excluded if using strong CYP3A4 inhibitors. If the patient is receiving a co-administered drug with moderate CYP3A4 and/or PgP inhibitors, the everolimus dose will be reduced by approximately 50% to maintain trough concentrations of 5 to 10 ng/mL. No moderate or strong CYP3A4 and/or PgP inhibitor will be added or discontinued during the study period.

• Patients TAKING one concomitant strong CYP3A4 inducer for seizure control (e.g., phenytoin, carbamazepine, phenobarbital) will be allowed in the study. Patients taking more than one strong CYP3A4 inducer will be excluded. For patients requiring a concomitant strong CYP3A4 inducer (an Enzyme-Inducing Antiepileptic Drug (EIAED), we will double the everolimus dose from that prescribed for patients not taking EIAEDs

Duration of administration	7 to 21 days
Reference therapy	Not applicable

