  - They will be instructed on the dosage and administration times of the study medication. All subjects will receive a specific quantity of tablets and they will be asked to record the time that each dose is given. They will be asked to bring back the medication that was not used so it can be reconciled with expected number of tablets to be used. This reconciliation will be logged on the drug reconciliation form, and signed and dated by the study team

6.2a Visit 2a – For patients taking the Everolimus for 3 weeks, at NYU CEC, they will have serum levels of everolimus drawn after 10-12 days on the medication. A trough level will be obtained. The study nurse or doctor will contact the patient with the results when available and will adjust the dose as described above. The nurse or doctor will also ask the patient to report any adverse events.

For active patients who reside outside of the NYC area and are unable to arrive at NYU CEC due to distance and travel issues prior to pre-admission testing, Visits 1 and 2 will be combined as one visit to be completed at least 7 days prior to Visit 3. For these patients with a combined Visit 1 and 2, this could mean a treatment window of 7-21 days depending both on which cohort they are in and how soon they can begin treatment.

Pre-surgical evaluation: Visit 2- Control Group

- Recent history will be reviewed for any change in medical status or change in intake of prescribed or over-the-counter medication.

CONFIDENTIAL

This document and information is the property of the NYU School of Medicine and Langone Medical Center. Do not disclose or use except as authorized in writing by the study IND sponsor

- Vital signs, physical and neurological examination
- A detailed seizure history during the prior week.
- Medication reconciliation.

Blood work: (pre surgical eval) CBC and C-reactive protein(CRP).

For control patients who reside outside of the NYC area and are unable to arrive at the study site due to distance and travel issues prior to pre-admission testing, Visits 1 and 2 will be combined as one visit and can be completed one day prior to Visit 3 if not earlier.

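### Section 5.3.2 applies fixed mg/m² steps to three different starting doses, so it yields an impossible dose for moderate-inhibitor patients with high levels and leaves unclear whether 5.1 or 5.3.2 governs

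*Combined protocol and SAP*

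**What the plan says.** Three starting doses follow from section 5.1 and the Study Summary.

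- **Standard:** "The starting dose of everolimus for treatment patients will be 4.5 mg/m"² once daily.
- **Moderate CYP3A4/PgP inhibitor:** "the everolimus dose will be reduced by approximately 50% to maintain trough concentrations of 5 to 10 ng/mL".
- **One strong inducer (EIAED):** 5.1 says "we will double the everolimus dose from that prescribed in Table 2". Table 2 lists no doses, but the Study Summary makes the base clear: "we will double the everolimus dose from that prescribed for patients not taking EIAEDs".

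Section 5.3.2 covers all 3-week patients, using one level drawn on days 10-12. It makes no change "If the result is in desired range (5-10 ng/ml"). Below that range, a level of 3-5 adds 2.0 mg/m²/day, and "if the value is less than 3 ng/ml, the recommendation will be dose will be increased by 3.0" mg/m²/day. Above it, 10-13 subtracts 2.0, and "If the value is above 13 ng/ml, the dose will be decreased by 3.0" mg/m²/day. The section ties the starting dose to body surface area and EIAED use. It does not mention inhibitors, does not scale the step to the current dose and sets no minimum.

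Other passages bear on the same patients:

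- Section 5.1 says that later dosing in both co-medication groups is individualised by drug monitoring when treatment lasts long enough.
- Section 5.2 lists all three co-medication groups and sends the reader to the Dose Adjustments section (numbered there as 5.3.1).
- The Visit 2a paragraph says "The study nurse or doctor will contact the patient with the results when available and will adjust the dose as described above".
- Tables 3 and 4 set a lowest level of 2.5 mg daily, but only for toxicity.
- Sections 5.1 and 5.3 give a general target of 5-15 ng/ml, where 5.3.2 uses 5-10.

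**The concern.** A step fixed in mg/m² means something different at each starting dose. Subtracting 3.0 takes a third off 9.0, takes two thirds off 4.5, and exceeds the whole of 2.25. A rule with no scaling and no floor can therefore give staff an instruction that cannot be carried out, in a group that the protocol admits.

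The passages that might resolve this point in different directions. Section 5.1 suggests individual judgement, while 5.2 and Visit 2a point to the described adjustments. A study nurse with a high level in an inhibitor patient would not know which to follow.

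The adjusted dose sets exposure when tissue is taken for the S6 measure. No further level is scheduled between the adjustment and the day of surgery.

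**Working it through.** **Inputs.** Starting doses are 4.5 (5.1), about 0.5 × 4.5 = 2.25 (5.1) and 2 × 4.5 = 9.0 mg/m²/day (5.1 and Study Summary). Steps and target are from 5.3.2. The half-life of 30 h is from section 1.5.

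**The plan's own timing figure.** 5 × 30 h = 150 h = 6.25 days, as section 1.5 states. At day 10 the level is at 1 − 2^(−240/30) = 99.6% of steady state. From day 12 to day 21 there are 9 × 24 / 30 = 7.2 half-lives. Comparing levels before and after the adjustment at steady state is therefore fair.

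**Step 1: new dose = starting dose + step. No assumption is needed.**

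| Start (mg/m²/day) | Level <3 | 3-5 | 10-13 | >13 |
|---|---|---|---|---|
| 2.25 (inhibitor) | 5.25 | 4.25 | **0.25** | **−0.75** |
| 4.5 (standard) | 7.5 | 6.5 | 2.5 | 1.5 |
| 9.0 (EIAED) | 12.0 | 11.0 | 7.0 | 6.0 |

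The halving is only approximate, so I varied it. A 40% reduction (start 2.7) gives 0.70 and −0.30; a 60% reduction (start 1.8) gives −0.20 and −1.20. The −3.0 step is negative whenever 4.5 × (1 − r) < 3.0, that is, for any reduction r over 33%.

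The 0.25 result is not practical either. The smallest tablet in 5.1 is 2.0 mg and tablets may not be broken. One tablet daily at 0.25 mg/m² implies a body surface area of 2.0 / 0.25 = 8 m²; one on alternate days implies 4 m².

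**Step 2 (secondary): predicted level = old level × (new dose / old dose)^b.** The documents give no dose-to-level relation. I assume b = 1 (proportional) and show 0.8 to 1.2.

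*EIAED patient, level below 3.* The dose ratio is 12 / 9 = 1.333, so at b = 1 the level ends below 3 × 1.333 = 4.0. At b = 0.8 and 1.2 the ceiling is 3.78 and 4.24. Reaching 5 from a level just under 3 needs b above ln(5/3) / ln(4/3) = 1.78.

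*Standard-dose patient, level between 13 and 15.* This patient is inside the 5-15 range of 5.1 and 5.3 but above the 5-10 range of 5.3.2. The dose ratio is 1.5 / 4.5 = 0.333. At b = 1, 13 becomes 4.33 and 15 becomes 5.0, so the level falls below both ranges. At b = 1.2 the results are 3.48 and 4.01. At b = 0.8 they are 5.40 and 6.23, so the level stays in range. The prediction disappears for the whole band once b is below ln(13/5) / ln 3 = 0.87.

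**The case against.** The strongest reply is that 5.1 already deals with these patients. Its individualised dosing applies to co-medicated patients treated long enough, and specific text can be read as overriding a general rule. The opening of 5.3.2, on the only planned adjustments, limits which patients are adjusted; it does not say that its steps exclude all others. Two of its rows are worded as recommendations. Visit 2a does not name 5.3.2. Section 5.1 allows alternate-day dosing for a reduction from 2.5 mg daily, and Tables 3 and 4 have a floor.

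This stands in part. The passages can be read together, so the fair charge against 5.1 and 5.3.2 is unclear precedence. But nothing states that 5.1 prevails, 5.3.2 has no inhibitor exception, the floor belongs to the toxicity tables, and alternate-day dosing cannot make a negative result positive.

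Three stronger readings are tempting, and the documents do not support them.

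- *That the rule cannot correct low levels in general.* With b = 1, standard-dose patients at 3.46-5 reach 5.0-7.2, EIAED patients at 4.09-5 reach 5.0-6.1, and inhibitor patients at 3-5 reach 5.7-9.4. Section 5.3.2 does not promise that one step restores the range.
- *That standard-dose patients below 3 are left short because the halved and doubled doses were ignored.* Their dose is neither. Any shortfall comes from the step size and sits on the boundary (3 × 1.667 = 5.0); at b = 1.2, levels of 2.71-3 would reach 5. I make no claim on it.
- *That a weak S6 result would be mistaken for drug failure.* The 21-day cohort is described as a safety-gated extension of duration, and the shorter cohorts have no level adjustment at all. The S6 t-test pools all treated patients, and a surgery-day level is drawn and correlated with S6, so under-exposure would be visible.

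**Conclusion.** The rule is wrong as written for inhibitor patients above range. It gives about 0.25 mg/m²/day at 10-13 ng/ml and −0.75 mg/m²/day above 13, by subtraction alone. The documents also leave open whether 5.1 or 5.3.2 governs 3-week patients on an inhibitor or an EIAED.

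The two predictions about levels are secondary and rest on proportionality. The EIAED result below 3 holds across the exponents tried. The standard-dose result at 13-15 holds at b = 1 and above but not at 0.8; the conflict between the 5-15 and 5-10 targets behind it needs no assumption.

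The reach is narrow: Table 2 puts 1-3 patients in the 21-day cohort, or 6 after an event (the text of 5.2 also says 6), among 9 treated. The number on a moderate inhibitor is not given, and the impossible dose also needs a level above 13. It should still be corrected before use, because a written dosing rule should not produce a dose that cannot exist in an admitted group.

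**What to change.** The sponsor should reconcile the passages that now pull apart: the starting doses and individualised dosing in 5.1, the cross-reference in 5.2, the target in 5.3, the steps and target in 5.3.2, the floor in Tables 3 and 4, and the instruction at Visit 2a. The amended text should state whether 5.1 or 5.3.2 governs 3-week patients on an inhibitor or an EIAED, and should no longer yield an impossible dose for inhibitor patients. How that is done, and with what values, is for the sponsor to decide; no dose or rule is proposed here.

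The cost is an amendment to the wording, with no extra patients, visits or blood draws.
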